#### **5.3** Criteria to Resume Treatment

Patients may resume treatment with study drug when the drug-related AE(s) resolve to Grade ≤1 or baseline value, with the following exceptions:

- Patients may resume treatment in the presence of Grade 2 fatigue;
- Patients who have not experienced a Grade 3 drug-related skin AE may resume treatment in the presence of Grade 2 skin toxicity;
- Patients with baseline Grade 1 AST/ALT or total bilirubin who require dose delays for reasons other than a 2-grade shift in AST/ALT or total bilirubin may resume treatment in the presence of Grade 2 AST/ALT or total bilirubin;
- Patients with combined Grade 2 AST/ALT and total bilirubin values meeting discontinuation parameters should have treatment permanently discontinued;
- Drug-related pulmonary toxicity, diarrhea, or colitis, must have resolved to baseline (Grade 1) before treatment is resumed. Patients with persistent Grade 1 pneumonitis after completion of a steroid taper over at least 1 month may be eligible for retreatment following discussion with the Study Chair or Co-Chair;
- Patients with drug-related endocrinopathies adequately controlled with only physiologic hormone replacement may resume treatment following discussion with the Study Chair or Co-Chair.

If the criteria to resume treatment are met, the patient should restart treatment at the next scheduled time point as per protocol. However, if the treatment is delayed past the next scheduled time point as per protocol, this time point should become day one of the subsequent cycle. If treatment is delayed or interrupted for > 6 weeks, the patient must be permanently discontinued from protocol therapy.

## 6. DOSE MODIFICATION FOR ADVERSE EVENTS

The Study Chair or Co-Chair must be notified of any dosage modification or use of myeloid growth factor.

## 6.1 Dose Modifications for Haematological Toxicity

Patients who experience Grade 4 thrombocytopenia (platelet count  $<25 \times 10^9/L$  or  $25,000/mm^3$ ) or Grade 4 neutropenia lasting at least five (5) days will be removed from protocol therapy. Patients with Grade 3 or 4 febrile neutropenia can remain on the study; however, dose should be held until toxicities return to baseline or  $\le$  grade 1.

## 6.2 Dose Modifications for Non-Haematological Toxicity

Patients who have any Grade 3 or Grade 4 non-hematological toxicity attributable to the investigational drug with the specific exclusion of the following, will be removed from the study:

- Grade 3 ALT that returns to levels that meet initial eligibility criteria or baseline within seven (7) days and does not require systemic immunosuppression;
- Grade 3 liver enzyme elevation, including AST/GGT that returns to baseline within 7 days and does not require systemic immunosuppression;
- Grade 3 or 4 serum electrolyte or mineral abnormalities responsive to supplementation;
- Grade 3 or 4 amylase or lipase abnormalities that are not associated with diabetes mellitus (DM), associated liver or gall bladder inflammation or clinical manifestations of pancreatitis;
- isolated Grade 4 amylase or lipase abnormalities that are not associated with symptoms or clinical manifestations of pancreatitis and decrease to < Grade 4 within 1 week of onset;
- Grade 3 rash/oral lesions that resolves to Grade  $\leq 1$  within seven (7) days;
- Grade 3 or 4 seizures (multiple seizures despite medical intervention or life-threatening seizures/status epilepticus) that may occur in the context of pseudo-progression;
- fever greater than 40°C of ≤24 hr. duration;
- Grade 3 fatigue that resolves to Grade  $\leq 2$  within 7 days;
- Grade 3 creatinine increase that resolves to Grade  $\leq 1$  or baseline within seven (7) days.

Patients who experience the following non-hematological toxicities attributable to protocol therapy will also be removed from the study:

- Grade 2 fever that does not resolve to Grade  $\leq 1$  within seven (7) days;
- Grade 2 uveitis, eye pain or blurred vision that does not respond to topical therapy and does not improve to Grade 1 prior to next scheduled dose;
- Grade 2 non-hematological toxicity requiring systemic immunosuppressive therapy. This includes, but is not limited to, autoimmunity of the lung, heart, kidney, bowel, CNS, pituitary or eye;
- Grade 2 endocrine toxicity requiring hormone replacement, with the exception of Grade
   2 hypothyroidism, thyroiditis and thyroid dysfunction adequately managed with thyroid hormone replacement;
- Grade 2 adrenal insufficiency;
- Grade 3 colitis or Grade 3 diarrhea attributable to protocol therapy of more the seven (7) days of duration.

Any non-hematological toxicity requiring greater than seven (7) days delay in therapy will be criteria for removal from the study. Other non-hematological toxicities attributable to the investigational drug will be dose adjusted as outlined below (see *Section 6.3 – 6.12*).

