## **6.9** Dose Modifications for Neurologic Adverse Events

Neurologic events	Management/Next Dose of Nivolumab					
≤ Grade 1	Continue protocol therapy.*					
Grade 2	Hold until resolution to baseline.* Resume with no change in dose.*					
Grade 3	Off protocol therapy.					
Grade 4	Off protocol therapy.					

\*Patients with any CNS events including aseptic meningitis, encephalitis, symptomatic hypophysitis, or myopathy, peripheral demyelinating neuropathy, cranial neuropathy (other than peripheral n. VII), GB syndrome, myasthenia gravis should be taken off protocol therapy.

**Recommended management:** See Neurologic Adverse Event Management Algorithm below (see *Section 6.9.1*).

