## 6.10 Immunotherapy Continuation Pending Confirmation of Progression

A decision of whether a patient should continue immunotherapy pending confirmation of radiographic disease progression should be established based on perceived benefits and risks as per the response criteria outlined in *Section 10*.

Continuation of immunotherapy might be considered pending follow-up imaging as long as patients are deriving apparent clinical benefit with minimal and acceptable toxic effects.

Immunotherapy should be interrupted for patients who require treatment with corticosteroids for evolving symptoms associated with cerebral oedema or who have more than mild treatment-related toxic effects such as at least grade 2 immune-related adverse events. Resumption of immunotherapy may be considered when symptoms resolve, steroids are reduced and the gadolinium enhancing tumour burden is classified as stable disease, partial response, or complete response on a follow-up scan, or when relevant treatment-related toxic effects have resolved to grade 1 or less or pre-treatment baseline. Decision to continue/discontinue immunotherapy should be made after discussion with the Study Chair or Co-chair.

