#### 7.11 Neurologic Toxicity

Neurologic symptoms can manifest as central abnormalities (e.g., aseptic meningitis, encephalopathy, or encephalitis) or peripheral sensory/motor neuropathies (e.g., Guillain-Barre Syndrome, myasthenia gravis complicated with sepsis and fatality). Early recognition and treatment of adverse neurologic reactions is critical to its management. Patients should be advised to seek medical evaluation if they notice impairment in motor function (e.g., weakness), changes in sensation (e.g., numbness), or symptoms suggestive of possible central nervous system abnormalities such as new headache or mental status changes. As neurologic symptoms can be common in patients with cancer, it is important that an evaluation/work-up distinguishes between non-drug-related causes (e.g., progression of disease, concomitant medications, or infection) and a possible drug-related events as the management can be quite different. The principal treatments for neurologic toxicity are dose delay, corticosteroids, and IV immunoglobulin as outlined in the safety algorithm (see *Section 6.9* and sub-sections). For high-grade related neurological symptoms, nivolumab should be discontinued.

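### Sections 6.2, 6.9, 6.9.1, 6.10 and 7.11 do not give one rule for Grade 3-4 seizures in pseudo-progression, and the 6.9 footnote conflicts with the rows it qualifies

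*Protocol*

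**What the plan says.** Section 6.2 sets the general rule: patients with Grade 3 or 4 non-haematological toxicity attributable to the drug, "with the specific exclusion of the following, will be removed from the study". The list that follows includes "Grade 3 or 4 seizures (multiple seizures despite medical intervention or life-threatening seizures/status epilepticus) that may occur in the context of pseudo-progression". The section ends with a time limit: "Any non-hematological toxicity requiring greater than seven (7) days delay in therapy will be criteria for removal from the study". It then sends other attributable toxicities to the organ tables in 6.3 to 6.12.

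The neurologic table in 6.9 has four rows. Grade 1 or lower reads "Continue protocol therapy". Grade 2 is hold until baseline, then resume. Grade 3 and Grade 4 each read "Off protocol therapy". An asterisk on the Grade 1 and Grade 2 entries leads to a footnote under which "Patients with any CNS events including aseptic meningitis, encephalitis, symptomatic hypophysitis, or myopathy", together with several named neuropathies and neuromuscular disorders, come off therapy. The 6.9.1 algorithm discontinues at Grade 3-4. Section 7.11 says: "For high-grade related neurological symptoms, nivolumab should be discontinued".

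Section 6.10 says: "Immunotherapy should be interrupted for patients who require treatment with corticosteroids for evolving symptoms associated with cerebral oedema". It allows resumption to be considered once symptoms, steroid dose and follow-up scan permit. Section 13.2 refers adverse events requiring removal to Section 7 only.

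**The concern.** A seizure during pseudo-progression is a neurologic event, so a site managing one has reason to open 6.9, 6.9.1 or 7.11. None of these mentions the exemption in 6.2 or points to it. The protocol plainly expects such events. It has a subsection on CNS pseudo-progression (6.9.2), advises considering debulking surgery to limit toxicity from it (4.2.2), and reports one case of hydrocephalus on this study judged probably related to nivolumab (1.6.6).

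The first stake is safety: instructions on whether treatment ends after a life-threatening seizure should not differ between sections of one protocol. The second is consistency of the endpoint. The iRANO rules in 10.9.2 look for confirmation of progression no sooner than three months after it is initially seen on imaging, and they do not count neurologic decline attributable to seizures as progression. Whether treatment has ended for good in the meantime may affect whether a delayed response is reached.

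**Working it through.** The plan states no figure on this point, so the check is a comparison of passages. Take a patient with a Grade 3-4 seizure, judged drug-attributable, in the context of pseudo-progression.

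| Section | What happens to this patient | Carries or cites the 6.2 exemption? |
|---|---|---|
| 6.2 | Not removed because of the grade | Source of the exemption |
| 6.9, Grade 3 and 4 rows | Off therapy | No |
| 6.9.1, Grade 3-4 | Therapy discontinued | No |
| 7.11 | Discontinued if high-grade and related | No |
| 6.10 | Interrupted if steroids are needed for oedema symptoms; may resume | No |
| 13.2 | Refers to Section 7, hence to 7.11 | No |

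**Does different wording remove the conflict?** Section 6.2 speaks of removal from the study, and 6.9 of coming off protocol therapy. But the Grade 2 row of 6.11 uses a 6.2 exception as an exception to coming off protocol therapy, and the Grade 3 pancreatitis row of 6.5 also cites 6.2. The protocol therefore treats the 6.2 list as governing treatment.

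**Does 6.2 rank itself above 6.9?** Its closing text sends other toxicities to 6.3-6.12. If an exempted seizure counts as other, it goes to 6.9, which stops treatment and cancels the exemption. If it does not, 6.2 governs, but nothing in 6.9 says so. Section 6.9.2 discusses steroids in CNS pseudo-progression and does not settle the question.

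**What does 6.2 actually permit?** It only avoids removal. Section 5.2 delays dosing for drug-related, non-skin events of Grade 2 or higher (fatigue and laboratory findings excepted), 6.2 removes the patient if the delay exceeds 7 days, and 6.10 may interrupt. The contrast is therefore a hold with the possibility of resuming against a permanent stop.

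**The footnote.** The asterisk sits on the entries that tell the site to continue (Grade 1 or lower) and to hold and resume (Grade 2). The text it leads to ends therapy, names CNS events in general before its list, and gives no grade. Read literally, one row says both continue and stop for a low-grade CNS event.

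**Timing, for illustration.** The first disease evaluation is at the end of cycle 1 with a window of minus 7 days, that is day 21-28. Taking three months as 91 days, a confirming scan for progression first seen then falls at 21 + 91 = day 112 to 28 + 91 = day 119, or later. A patient stopped after the day-15 dose meets the 30-day off-study criterion in 13.3 at 15 + 30 = day 45. However, 8.2 schedules an end-of-treatment assessment and three-monthly scans for a year, so day 45 need not be the end of observation.

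**The case against.** The strongest reply is that 6.2 can be read as applying first, with the organ tables covering what remains. Section 6.9.1 is headed as recommended management, and contact with the Study Chair or Co-Chair is built in: 6.10 requires discussion before continuing or discontinuing, the 8.2 calendar notes require it for delays and omissions, and Section 6 requires notice of dosage modifications. A missing cross-reference is also weak evidence of intent, because the Grade 3-4 liver row of 6.5 likewise omits the 6.2 exceptions for liver enzymes. The footnote mostly lists specific diagnoses, several of them outside the CNS, and may have been meant narrowly.

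Much of this stands. Central consultation should limit divergence between sites, and the narrow reading of the footnote is plausible. But the order of precedence is nowhere stated, and the footnote's words do not confine it to the named diagnoses.

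A reader might go further and infer that a site following 6.2 simply keeps dosing. It does not: 5.2, the 7-day limit and 6.10 all restrict dosing. A reader might also infer that brain-tumour patients are stopped before response can be judged. That is not shown, given the follow-up scans in 8.2 and the provision in 10.4.1 (written for solid tumours) that assessments after discontinuation can count towards best response.

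**Conclusion.** The contradiction is in the text and needs correcting. For a drug-attributable Grade 3-4 seizure in pseudo-progression, 6.2 spares the patient from removal, 6.9 and 6.9.1 end treatment, 7.11 ends it for high-grade related symptoms, and 6.10 offers interruption with possible resumption. The footnote is a second, separate conflict within 6.9, on its literal reading.

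Its effect on the response rate cannot be sized. One might apply the 36-48% brain-tumour share that Section 1.1 gives for CMMRD to the 30 places in Cohort B (0.36 × 30 = 10.8; 0.48 × 30 = 14.4) and speak of 11 to 14 patients. That would count all brain-tumour patients, not those with such seizures. Cohort B is also defined by mutation burden, not by CMMRD. Nor can a number of lost doses be claimed, since the alternative path is itself a hold and the three-month clock runs from the first radiographic progression, not from the seizure. What remains is a safety and consistency fault with a possible, unquantified bearing on delayed CNS responses.

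**What to change.** Reconcile 6.2, 6.9 with its footnote, 6.9.1, 6.10, 7.11 and the pointer in 13.2 so that they give a single rule for Grade 3-4 seizures in the context of pseudo-progression, with each section either stating that rule or pointing to where it stands. In the same edit, state which events the 6.9 footnote covers and at which grades it overrides the row entries. Which clinical rule applies, and how wide the footnote should be, are for the sponsor to decide.

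The cost is a wording amendment to a few table entries, one footnote and some cross-references, through the usual amendment review (14.2, 17.1). It adds no procedures, visits or patients.

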## **5.2** Criteria for Starting Subsequent Cycles

A cycle, consisting of two (2) doses every 14 days +/- 2 days, may be repeated every 28 days if the patient has not met any of the criteria for removal from therapy.\*

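### Section 6.2 removes patients whom 5.3, 6.5, 6.7, 6.13.1, 7.5 and 7.14 let resume nivolumab after steroids, and Grade 3 nausea/vomiting is removal in 6.2 but hold-and-resume in 6.6

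*Protocol*

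**What the plan says.** Protocol 6.2 contains three removal rules that matter here.

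- Length of delay: "Any non-hematological toxicity requiring greater than seven (7) days delay in therapy will be criteria for removal from the study".
- Immunosuppression: it removes "Grade 2 non-hematological toxicity requiring systemic immunosuppressive therapy" when attributed to protocol therapy, with a non-exhaustive list that names lung, kidney and bowel.
- Severity: drug-attributable Grade 3 or 4 non-haematological toxicities, "with the specific exclusion of the following, will be removed from the study". The list of exclusions covers, among others, short-lived Grade 3 rash and fatigue, but not nausea or vomiting.

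Toxicities not caught by these rules "will be dose adjusted as outlined below", in 6.3 to 6.12.

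Other sections provide for resumption. Section 5.3 says "Patients with persistent Grade 1 pneumonitis after completion of a steroid taper over at least 1 month may be eligible for retreatment", after discussion with the Study Chair or Co-Chair. Section 6.5 holds Grade 2 liver elevation until any corticosteroid management is finished. Sections 6.7 and 7.5 let Grade 2 pneumonitis resume once steroids are finished. Section 6.13 has no table of its own and refers to 6.13.1, which resumes nivolumab after methylprednisolone and a taper for Grade 2 creatinine rise. Section 7.14 allows resumption after a taper for suspected immune-related reactions. The algorithms in 6.4.1, 6.5.1, 6.6.1, 6.7.1 and 6.11.1 contain similar steps.

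Section 5.3 also sets a general limit: "If treatment is delayed or interrupted for > 6 weeks, the patient must be permanently discontinued from protocol therapy".

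**The concern.** For the same event, one section ends nivolumab and another continues it. These patients have no known curative option (4.2.2), so the decision matters to the individual. For the analysis, drug exposure, the count of removals for toxicity and the description of tolerability, which is a secondary objective (2.2), would depend on which section a site happened to follow. The events concerned are liver, lung, bowel and kidney toxicity, for which the protocol provides its own management algorithms.

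**Working it through.** **Rules side by side**

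| Event | Section 6.2 | Other operative text |
|---|---|---|
| Persistent Grade 1 pneumonitis after a taper of at least 1 month | Removed: delay over 7 days | 5.3: may be retreated |
| Grade 2 liver elevation needing steroids | Removed: Grade 2 with systemic immunosuppression | 6.5: hold until steroids are finished |
| Grade 2 pneumonitis treated with steroids | Removed: same rule, lung named | 6.7 and 7.5: resume once resolved and steroids finished |
| Grade 2 creatinine rise treated with methylprednisolone | Removed: same rule, kidney named | 6.13/6.13.1: taper at least 1 month, then resume |
| Other immune-related reaction treated with steroids | Removed if Grade 2, or if the delay exceeds 7 days | 7.14: may resume after the taper |
| Grade 3 nausea/vomiting, drug-attributed, Grade 1 or less within 7 days | Removed: not in the exclusion list | 6.6: hold, then resume at the same dose |

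The liver, lung and kidney rows conflict through the immunosuppression rule alone, with no day count needed.

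**Can a taper of at least 1 month fit a 7-day limit on delay?**

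Inputs: dosing is "two (2) doses every 14 days +/- 2 days" (5.2); the taper lasts at least 1 month (5.3, 6.5.1, 6.6.1, 6.7.1, 6.13.1); the limit is 7 days (6.2). Assumptions: a month is 28 days, with 31 as the upper range, and delay is counted from the missed dose.

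- Last dose on day 0; next dose due on day 14, or day 16 at the end of its window.
- Toxicity appears on day d (0 to 14); steroids run s days (s at least 0) before the taper. The taper ends no earlier than day d + s + 28.
- Delay past day 14: (d + s + 28) − 14 = d + s + 14, at least 14 days. Past day 16: d + s + 12, at least 12 days.
- With a 31-day month the minima are 31 − 14 = 17 and 31 − 16 = 15 days.

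All exceed 7 days, even with toxicity and taper starting on the day of the last dose. If delay were counted from the last dose instead, the minimum would be 28 days, so the conclusion does not depend on that choice. Section 5.3 adds that "the patient should restart treatment at the next scheduled time point as per protocol", which on the 14-day schedule puts the earliest restart at day 28.

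**Diarrhoea/colitis.** Section 6.6 takes Grade 3 events, and any patient who needs steroids, off treatment. Section 6.6.1 allows resumption after the taper for Grade 2 treated with steroids and for Grade 3. This conflict exists independently of 6.2.

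**Nausea/vomiting.** The hand-off in 6.2 to the organ tables covers only toxicities not already dealt with. A drug-attributed Grade 3 event is already caught by the severity rule, so the hand-off does not rescue it. Rash and fatigue with a similar 7-day recovery pattern are excluded, which suggests an oversight. The mismatch does not arise for events not attributed to nivolumab.

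**The case against.** A reader might infer that 7 days in 6.2 against 6 weeks in 5.3 is itself the contradiction, and that 5.3 permits any delay of 8 to 42 days. The text does not support that. The 6-week limit applies to every delay or interruption, including intercurrent illness (5.2) and febrile neutropenia (6.1), and 5.3 allows restart only when its toxicity criteria are met. A tighter limit for one class of toxicity under a general ceiling is coherent. What is not coherent is the set of resume-after-steroid steps.

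Second, 6.4.1, 6.5.1, 6.6.1, 6.7.1 and 6.11.1 are headed as recommendations, and several of their resumption steps defer to the protocol, so they can be read as subject to 6.2. That stands, and it is why the point rests on 5.3, 6.5, 6.7, 6.13, 7.5 and 7.14. Section 6.13.1 carries the same heading, but 6.13 makes it the only source of renal dose modifications.

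Third, the 7 days might mean persistence of the toxicity, with taper time not counted. Section 6.13.1 hints at this: creatinine elevation beyond 7 days is escalated, and otherwise the patient tapers and resumes. But 6.2 speaks of delay in therapy, 6.7.1 allows two weeks for pneumonitis to improve, and this reading leaves the immunosuppression rule in conflict anyway.

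Fourth, delays are to be discussed with the Study Chair or Co-Chair (8.2), who must also be told of dose modifications (section 6). This limits divergence between sites but does not say which rule applies.

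**Conclusion.** The conflict is real and lies in current operative text. Section 6.2 removes patients whom 5.3, 6.5, 6.7, 6.13/6.13.1, 7.5 and 7.14 allow to resume after steroids. Section 6.6.1 contradicts 6.6 on diarrhoea/colitis, and Grade 3 nausea/vomiting is handled in opposite ways by 6.2 and 6.6. The minimum overrun is 12 to 14 days against a limit of 7, assuming a 28-day month and delay counted from the missed dose (15 to 17 days with a 31-day month).

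It should be corrected, but its reach is limited. The protocol gives no rates for these events, so the number of patients affected is unknown. Adverse events are still captured to the Safety Visit or 100 days after discontinuation, whichever is later (12.6), so the point does not imply lost safety data. Nor does it touch the Simon design figures in section 11.

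**What to change.** 1. State in 6.2 which rule governs when it and an organ-specific section differ. There are two consistent options.
   - List in 6.2 the specific events exempt from the 7-day and Grade 2 immunosuppression rules, for example Grade 2 hepatic, Grade 1–2 pneumonitis and Grade 2 renal events that resolve, with the 5.3 6-week ceiling applying to them. Any resume-after-steroid step not covered by the list should then be removed.
   - Or state that 6.2 prevails, and remove the resume-after-steroid steps in all of 5.3, 6.4, 6.4.1, 6.5, 6.5.1, 6.6.1, 6.7, 6.7.1, 6.10, 6.11.1, 6.13.1, 7.5 and 7.14.

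   The choice is clinical, because the first option relaxes a paediatric safety stop; it belongs to the sponsor's clinicians.
2. Align 6.6.1 with 6.6, so that Grade 3 diarrhoea/colitis, and any diarrhoea/colitis needing steroids, is off treatment.
3. Add to the 6.2 exclusions Grade 3 nausea/vomiting that resolves to Grade 1 or less within 7 days.

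The cost is a protocol amendment with ethics and regulatory approval (14.2, 17.1). No extra procedures or patients are needed.

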## **6.6** Dose Modifications for Gastrointestinal Adverse Events

Diarrhoea/	Management/Next Dose of Nivolumab	
Colitis		
Grade 1	Continue protocol therapy and treat symptomatically.	
Grade 2	• May observe and treat symptomatically for seven (7) days. If persists greater than seven (7) days, then off protocol therapy.	
Grade 3	Off protocol therapy.	
Grade 4	Off protocol therapy.	

Patients who require steroids should be taken off study treatment.

Evaluation for all patients for additional causes includes C. diff., acute, self-limited infectious, foodborne illness, ischemic bowel, diverticulitis, and IBD.

**Recommended management:** See GI AE management Algorithm below (see *Section 6.6.1*).

Other GI	Management/Next Dose of Nivolumab
Nausea/ Vomiting	
Grade 1	No change in dose.
Grade 2	
 
Hold pending evaluation for gastritis duodenitis and other immune adverse events or other causes. Resume at same dose level if resolution to ≤ Grade 1 within seven (7) days.
 

Grade 3	
 
Hold pending evaluation until ≤ Grade 1. Resume at same dose level. If symptoms do not resolve within seven (7) days with symptomatic treatment patients should go off protocol therapy
 

Grade 4	Off protocol therapy  Off protocol therapy  Office of the state o

Patients with grade 2 or 3 N-V should be evaluated for upper GI inflammation and other immune related events. Recommended Gastrointestinal Adverse Event Management Algorithm

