# **6.6.1** Recommended GI Adverse Event Management Algorithm

Opiates/narcotics may mask symptoms of perforation. Infliximab should not be used in cases of perforation or sepsis.

Toxicity (CTCAE	Management	Follow-up
v.4.03)  Grade 1  Diarrhea: < 4 stools/ day over baseline.  Colitis: asymptomatic.	

Continue protocol therapy

Symptomatic treatment

	
 
Close monitoring for worsening symptoms.
 
Educate patient to report worsening immediately.
 
If worsens:
 
Treat as Grade 2 or 3/4
 

Grade 2 Diarrhea: 4-6 stools/ day over baseline; IV fluids indicated <24hrs; not interfering with ADL. Colitis: abdominal pain; blood in stool.	
 
Nivolumab should be withheld per protocol.
 
Symptomatic treatment
 
	
 
Resume protocol therapy
 
If persists > 5-7 days or recurs:
 
0.5-1.0mg/kg/day         methylprednisolone or oral         equivalent
 
When symptoms improve to         grade 1, taper steroids over at         least 1 month
 
Consider prophylactic         antibiotics for opportunistic         infections
 
Resume nivolumab per         protocol.
 
If worsens or persists > 3-5 days         with oral steroids:         
 
Treat as Grade 3 or 4 and

Grade 3 Diarrhea: ≥ 7 stools/ day over baseline; incontinence; IV fluid ≥ 24 hours; interfering with ADL Colitis: severe abdominal pain, medical intervention indicated, peritoneal signs	
 
Hold protocol therapy
 
Corticosteroids at dose of 1-2 mg/kg/day methylprednisolone IV or IV equivalent
 
Add prophylactic antibiotics for opportunistic infections
 
Consider lower endoscopy
 
Nivolumab should be withheld and corticosteroids initiated at
 
	permanently discontinued.  If improves:  Continue steroids until grade 1, then taper over at least 1 month.  Upon improvement, nivolumab may be resumed after corticosteroid taper. If worsening or no improvement occurs despite initiation of corticosteroids, nivolumab must be permanently discontinued.

	a dose of 1-2 mg/kg/day methylprednisolone equivalents.	If persists > 3-5 days or recurs  after improvement:  • Consider adding Infliximab 5  mg/kg (if no contraindication).  Note: Infliximab should not be used in cases of perforation or sepsis.

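### Section 6.2 orders removal for toxicities after which 6.6.1, 6.11.1 and 5.3 allow nivolumab to restart, and no rule says which governs

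*Protocol*

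**What the plan says.** Section 6.2 sets three removal rules.

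- **Grade 3-4.** Patients with such a non-haematological toxicity attributable to nivolumab, "with the specific exclusion of the following, will be removed from the study". The exclusions are mostly laboratory changes and events that settle within days.
- **Grade 2 with immunosuppression.** A second list includes "Grade 2 non-hematological toxicity requiring systemic immunosuppressive therapy. This includes, but is not limited to, autoimmunity of the lung, heart, kidney, bowel, CNS, pituitary" and the eye. The same list adds "Grade 3 colitis or Grade 3 diarrhea attributable to protocol therapy of more the seven (7) days of duration".
- **Delay.** "Any non-hematological toxicity requiring greater than seven (7) days delay in therapy will be criteria for removal from the study".

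Other toxicities attributable to the drug "will be dose adjusted as outlined below", with a pointer to 6.3-6.12.

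Section 6.6 takes Grade 3 and 4 diarrhoea or colitis off protocol therapy and adds: "Patients who require steroids should be taken off study treatment". The Grade 3 row of 6.6.1 says instead: "Continue steroids until grade 1, then taper over at least 1 month", and then "Upon improvement, nivolumab may be resumed after corticosteroid taper. If worsening or no improvement occurs" on steroids, in which case the drug stops for good.

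The 6.11 table takes hypophysitis and adrenal insufficiency off therapy from Grade 2, with a thyroid exception borrowed from 6.2. The 6.9 footnote takes symptomatic hypophysitis off therapy. The note under 6.11.1 lets nivolumab resume after a corticosteroid taper for symptomatic hypophysitis. Section 5.3 lets persistent Grade 1 pneumonitis be retreated after a taper of at least one month, following discussion with the Study Chair or Co-Chair, and discontinues permanently only when a delay passes six weeks.

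**The concern.** These are dosing instructions for children and young adults with immune toxicity, and two sites could each follow the protocol and do opposite things. One reads 6.2 and removes the patient; the other reads an algorithm or 5.3 and redoses after steroids. The first risk is to the patient. The second is to the data: how many patients stop for toxicity bears on the secondary safety and tolerability objective, and it would depend on which section a site applied.

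**Working it through.** The plan gives no figure to reproduce, so the check is to set the texts side by side, with one line of arithmetic on the delay limit.

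**Delay limit.** Inputs: dosing every 14 days (5.1); removal beyond 7 days' delay (6.2); discontinuation beyond 6 weeks, that is 6 × 7 = 42 days (5.3); taper of at least one month, taken at its shortest as 28 days. Count delay from the missed due date. In the most favourable case the taper starts on the day of the last dose and nothing precedes it, so the earliest restart is day 28 against a due date of day 14: 28 − 14 = 14 days late. That is already beyond 7. A later steroid start, a steroid course before the taper, or waiting for the next scheduled time point as 5.3 asks can only lengthen it. Every restart after a completed one-month taper therefore breaks 6.2. The two ceilings differ by 42 / 7 = 6 times; a toxicity delay of 8 to 42 days is removal under 6.2 and within the limit in 5.3.

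**Clear conflicts.**

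1. *Grade 3 diarrhoea or colitis.* 6.6: off at Grade 3, and off if steroids are needed. 6.6.1: steroids, taper, possible restart. These patients also fail the 7-day rule. 6.2 is itself unclear here: the event is not among the Grade 3-4 exclusions, yet it is listed again only when it lasts more than 7 days. On either reading the 6.6.1 restart fails, because the taper alone exceeds the delay limit.
2. *Symptomatic hypophysitis.* 6.9 footnote and 6.11 table: off. 6.2: removal at Grade 2 if systemic immunosuppression is needed, pituitary named. 6.11.1 note: restart after taper.
3. *Retreatment after a long taper.* 5.3 allows it for persistent Grade 1 pneumonitis; the 7-day rule in 6.2 has already removed that patient.

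**Partial conflicts.**

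4. *Grade 2 pneumonitis.* 6.7 and 7.5 resume after steroids, but only if lymphocytic pneumonitis has been excluded. 6.2 names autoimmunity of the lung. The overlap is therefore not complete, although 7.5 is written about nivolumab-related pneumonitis and does not separate the two groups cleanly.
5. *Liver.* The 6.5.1 footnote allows delay instead of stopping in its Grade 3-4 row, up to 8 × ULN for AST/ALT or 5 × ULN for bilirubin. 6.2 excuses Grade 3 ALT and other liver enzyme rises that recover within 7 days without systemic immunosuppression. For those patients the footnote and 6.2 agree, and the 6.5 table, which stops all Grade 3-4, is the outlier. The footnote conflicts with 6.2 only for bilirubin, slower recovery, or cases needing immunosuppression.

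**The case against.** The best defence is that 6.2 plainly governs. It sends only the remaining toxicities to 6.3-6.12; the 6.11 table and the 6.5 pancreatitis table both defer to it; its rules are worded for any toxicity and name the kidney, so they reach events managed in 6.13 and Section 7; and the x.x.1 algorithms are headed as recommendations. The Study Chair or Co-Chair is also notified of dose modifications (Section 6), consulted on delays (8.2 footnote 2) and consulted under 7.14. The six-week ceiling in 5.3 could be read as a general limit that also covers delays unrelated to non-haematological toxicity.

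Much of this stands as evidence of intent, and it is why the fix below lets 6.2 prevail. It does not remove the contradiction. No sentence states precedence; 5.3, the 6.7 table and 7.5 are not recommendations; 13.2 item 2 points to Section 7 alone for removals; and the Chair who is consulted faces the same two rules. A general reading of the six-week ceiling does not rescue the pneumonitis allowance in 5.3, because that restart follows a taper.

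A reader might infer more than the text supports. Not every resumption clause conflicts: 6.4.1, 6.13.1 and the Grade 2 row of 6.6.1 resume only as the protocol allows, and 7.14 conflicts by implication only. Nor can pneumonitis or the hepatic footnote be called flat contradictions, for the reasons given above.

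**Conclusion.** The protocol is wrong as written on three pairs (Grade 3 diarrhoea/colitis, symptomatic hypophysitis, retreatment after a taper under 5.3) and partly so on two more (Grade 2 pneumonitis, Grade 3-4 liver). The size is a 7-day against a 42-day delay limit, with any restart after a completed one-month taper at least 14 days late. This assumes that delay runs from the missed due date, that a month is at least 28 days, and that removal from the study in 6.2 includes stopping nivolumab. How many patients would be affected cannot be derived from the protocol.

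It would be tempting to carry this to the primary endpoint. The document does not support that: the Simon designs count CR and PR, patients already evaluable are not replaced on withdrawal (13.1), and for solid tumours 10.4.1 lets assessments after therapy ends count towards best response until new treatment starts. Type I error and power are untouched. The point is about patient safety and consistent reporting of toxicity stops, and it should be corrected.

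**What to change.** - State in 6.2 that its removal criteria take precedence over all resumption wording in 5.3, Section 6 and Section 7.
- Change the Grade 3 row of 6.6.1 and the hypophysitis note in 6.11.1 to off therapy.
- Limit the 6.5.1 footnote to cases that meet a 6.2 exclusion, and give the 6.5 liver table the same deferral to 6.2 exceptions that the 6.11 table carries.
- Make 13.2 item 2 cite Sections 6 and 7.
- List in 6.2, as explicit exceptions to each removal rule they would otherwise meet, any restarts the sponsor wants to keep: for example Grade 2 pneumonitis with lymphocytic pneumonitis excluded, or steroids for CNS pseudo-progression under 6.9.2 and 6.10.
- Let the sponsor decide whether the over-7-days qualifier for Grade 3 colitis/diarrhoea in 6.2 stays. That is a clinical choice, and its deletion is not required.

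The cost is wording only, with no new visits or procedures. The downside is that some patients who might have restarted after steroids would stop, as 6.2 already requires. Patients given steroids for CNS pseudo-progression could be caught as well unless the exception is written, so that item should not be left open.
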